12.0 Participant Information

12.1 Subject Population

140 participants will be recruited for the study. Participants will be active duty service members with a history of mTBI based on the DoD diagnostic criteria (Management of Concussion, 2009) who have persistent elevated neurobehavioral symptoms more than 1 month from injury compared to published normative data (Soble et al., 2014). mTBI diagnosis will be confirmed through a structured clinical interview using the Ohio State University Traumatic Brain Injury Identification Method (OSU TBI-ID) (Corrigan & Bogner, 2007) as well as through a review of participant electronic medical records (e.g., MHS GENESIS).

Participants will include male and female active duty service members who are between the ages of 18 and 55. Specific efforts will be made to recruit female participants given our site is an active duty military base predominantly of males.

12.2 Age Range – 18-55

12.3 Gender – Male, Female, Other

12.4 Special categories, check all that apply – Active Duty Military Personnel, Wounded Warriors, Pregnant Women, Fetuses, and Neonates

12.5 Inclusion Criteria

Male or female ages 18 to 55 years.

History of mTBI: Participants will have a history of at least one mTBI sustained >1 month previously based on criteria of the DoD diagnostic criteria. This specifies an external force to the head which resulted in physiological dysfunction of the brain as manifested by one or more of the following acute symptoms:

- o Any loss of consciousness (not to exceed 30 minutes)
- o Any loss of memory for the events immediately before or after the injury (not to exceed 1 day)

o Any alteration of consciousness or change in mental state (not to exceed 24 hours)

Persistent Post-Concussive Symptoms: Participants will endorse atypical neurobehavioral symptomatology compared to published normative data (Soble et al., 2014). Atypical symptoms will be defined as less than the 25th percentile

12.6 Exclusion Criteria

- History of TBI (any severity) within 1 month of enrollment.
- History of a moderate, severe, or penetrating TBI as defined by DoD/VA guidelines.
- Current substance use disorder.
- History of a neurological disease other than mTBI such as multiple sclerosis, cerebral vascular accident, brain tumor, neurodegenerative disease, or neuro-motor disorder.
- Current, active suicidal or homicidal ideation.
- Impaired decision-making capacity.
- An acute orthopedic injury that limits your capacity to complete study procedures as determined by the study Physical Therapist, PI, and/or medical record review.

- EAS date within 6 months of study enrollment.

13.0 Recruitment and Consent

13.1 Please describe the recruitment process, including how subjects will be identified and selected for the study

Potential participants will be identified through clinician referrals, responding to IRB-approved study advertisement flyers, through in-person recruitment, and/or word of mouth.

In-person recruitment to occur primarily at:

1. Marine Corps Base Camp Pendleton facilities
2. NHCP and MTF site clinics where SMs, with and without TBI, may receive care (e.g. post-deployment clinics, mental health clinics, pain clinics, PM&R clinics, primary care clinics, neurology clinics)

Additional methods of recruitment include:

1. Posting of recruitment flyers across Camp Pendleton facilities
2. Websites where SMs may find information about research studies will advertise the study with a posted study description, contact information, and a link to the study flyer.

ISC clinicians will be educated about the study by one of the study team members during regularly scheduled clinic meetings, through one-on-one conversations, and through email communications. They will be asked to refer patients who meet basic criteria and express an interest. The clinicians will provide eligible patients with a brief description of the study and ask if they would like to be contacted by a researcher for more information. If the patient is interested, the clinician will inform the appropriate researcher. The researcher will then contact the patient by phone to provide an overview of the study, answer questions, and schedule a screening and consent session.

If a participant self-refers, by contacting the research team in response to a study advertisement or from hearing about the study from someone (e.g., previous participant, friend, coworker, etc.), the research coordinator will take extra care to screen the candidate by verifying information in his/her medical record.

Clinicians and researchers will be responsible for providing potential subjects with an accurate depiction of the study's potential benefits. Subjects will be given an unbiased description of the treatment plan offered by the study. They will be informed that they may or may not benefit directly from the study, and they will not be receiving direct compensation.

Flyers will be disseminated at the ISC, NHCP, and/or Marine Corps Base Camp Pendleton facilities to extend the reach of recruitment efforts. The flyers will provide a brief description of the study, the study population, and provide direct contact information for the researchers. The material will not be coercive, and the participants will be informed that the study is not command-directed.

13.2 Compensation for Participation

Participants will be informed that they will not receive compensation for participation. A certificate of appreciation will be given at study completion to thank participants for their time.

13.3 Please describe the pre-screening process. If no pre-screening, enter Not Applicable in the text editor

Clinicians will have instructions to refer patients who have had a mTBI defined by DoD criteria (Department of Veterans Affairs and Department of Defense, 2016), are 1 or more months post-injury, and have been experiencing persistent symptoms dating from the event. Participants will confirm these facts with a researcher during the informed consent process. This screening conversation will also check for exclusionary conditions (see Section B). Researchers involved in the screening/consent process will have access to the patient's medical history through the electronic medical records system, MHS GENESIS. If any aspect of eligibility is in question or in the case of self-referral, researchers will have NHCP IRB approval to search the patient's record and ascertain eligibility.

13.4 Consent Process: Revised Common Rule, Section 219.116: General requirements for informed consent, whether written or oral, are set forth in this paragraph and apply to consent obtained in accordance with the requirements set forth in paragraphs (b) through (d) of this section. Broad consent may be obtained in lieu of informed consent obtained in accordance with paragraphs (b) and (c) of this section only with respect to the storage, maintenance, and secondary research uses of identifiable private information and identifiable biospecimens.

- **No**

Please explain the consent process:

After a potential participant expresses interest in the study, a researcher from the study with relevant credentials and human subjects training will provide a thorough description of the study and screen the candidate for inclusion and exclusion criteria. If the participant is a suitable fit for the study, the researcher will then go over each page of the Informed Consent form with him/her and answer any questions that arise during their discussion. The participant will be informed that at any time during the consent process and throughout the study they are free to ask questions of any of the researchers or contact a PI directly.

Participants will be given time to review the consent form and consider whether they would like to participate. They will be permitted to take the consent form home and/or consult others (friends, doctors, co-workers, etc.) prior to making their decision to participate or not. If the researcher conducting consent is unsure about a question s/he receives from a participant, the researcher will contact the PI for clarification. Consents will be conducted in person between 0800 and 1600 Monday through Friday, excluding holidays, in a private room at the Intrepid Spirit Center at NHCP. In order to monitor continuing consent, at the immediate and 3-month follow-up sessions, participants will be asked whether they wish to continue with their participation in the study.

13.5 DoDI 3216.02 requires an ombudsman to be present during recruitment briefings when research involves greater than minimal risk and recruitment of Service members occurs in a group setting. If applicable, you may nominate an individual to serve as the ombudsman – **N/A**

13.6 Withdrawal from Study Participation

Explain the process for withdrawal and specify whether or not the subjects will be given the opportunity to withdraw their data their data/specimens in the event they wish to withdraw from the study

Participants may withdraw consent at any time and stop participating in this research study without affecting their eligibility for care or any other benefits to which they are entitled. In order to withdraw, participants must notify the point of contact for this study, [name], PhD at [contact]. If participants are receiving treatment as part of this research study, they will no longer be eligible for such research-related treatment and will be advised to contact their personal physician to discuss medical treatment for their condition.

Withdrawing consent to participate in this research will not fully revoke the HIPAA Authorization Form to use/disclose protected health information. To make that revocation, participants must send a letter to the principal investigator as discussed in the HIPAA Authorization Form.

The Principal Investigator of this research study may terminate participation in this research study at any time if he determines this to be in a participant's best interest, or if a participant is unable to comply with the procedures required, or if they no longer meet eligibility criteria.

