Hypothesis 1: There will be a greater reduction in the Neurobehavioral Symptoms Inventory (NSI) from pre- to post-SAET compared to the control condition. A similar finding will continue from immediate to 3 month post-SAET.

Secondary Aims:

Sub-aim 1 Cognitive Status: To determine if SAET is effective at improving cognitive impairment among SMs with persistent complaints from mTBI.

Sub-hypothesis 1: There will be a greater decrease in the Global Deficit Scores (GDS; an overall measure of cognitive impairment) post SAET in comparison to the control condition.

Sub-aim 2 Physiological Adaptation: To measure physiological adaptation associated with SAET compared to the control condition.

Sub-hypothesis 2: SAET will be associated with improved cerebrovascular blood flow regulation, as measured by Transcranial Doppler and improved cardiovascular function, as measured by changes in heart rate variability (HRV) and estimated maximal oxygen consumption (est. VO₂ max) compared to the control condition.

Sub-aim 3 Warfighter Performance: To determine if SAET participants will have improved locomotion and a higher level of occupational performance compared to the control condition.

Sub-hypothesis 3: SAET participants will have improved locomotion and physical performance (based on the Marine Corps Combat Fitness Test(CFT)) and higher ratings of occupational performance (based on supervisor ratings on the Checklist of Military Activities of Daily Living [M-ADL]) after completion of treatment and 3 months post-treatment compared to the control condition.

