11.5 Please provide a justification for your sample size

With 140 participants, 70 in each intervention arm, we will be able to potentially detect a significant difference in change in neurobehavioral symptoms between the two physical activity interventions (i.e., SAET and SCG) with an 85% power using a two-tailed test and an alpha of 0.05. This estimate is based on similar research on a civilian population (Kaplan, Vasterling, & Vedak, 2010), and takes into consideration a 20% attrition. The 140 participants recruited will suffice to address the research question for secondary aims given the same parameters.

11.6 Data Analysis Plan Complete description: Background, Objectives, Design, Step by Step how the project is going to be done

Primary Aim: Neurobehavioral symptoms: Primary analyses will evaluate whether change in neurobehavioral symptoms from pre- to immediate post-treatment, as well as from immediate post-treatment to 3 months post-treatment, differ between the physical activity interventions. In addition to assessing change in symptoms continuously, we will also evaluate reaching a clinically-relevant change in neurobehavioral symptoms (defined as a change in NSI score of 8 points) (Belanger et al., 2016). Secondary analyses will investigate differences in overall change in neurobehavioral symptoms from pre-treatment to 3 months post-treatment between the interventions using multilevel mixed-effect modeling. This approach will take into consideration between-subject variance based on randomized group, as well as within-subject variance for repeated measures. Analyses will be based on intention to treat (ITT).

Sub-Aim 1: Cognitive Performance: Similar statistical approach as Aim 1 will be conducted for Sub-Aim 1. Exposure will remain as the type of intervention (i.e. SAET vs. SCG); however, outcome will be on global deficit score based on the cognitive test scores.

Sub-Aim 2: Physiological Adaptation: Analysis of Variance (ANOVA) will be utilized to determine differences in continuous variables of physiological adaptation (i.e., cerebrovascular flow, improved cardiovascular health) between interventions.

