14.0 Risk and Benefits

14.1 Risk of Harm

Identify all research-related risks of harm to which the subject will be exposed for each research procedure or intervention as a result of participation in this study. Consider the risks of breach of confidentiality, psychological, legal, social, and economic risks as well as physical risks. Do not describe risks from standard care procedures; only describe risks from procedures done for research purposes

The following are some foreseeable risks:

Prescribed Exercise Program: Participants may experience fatigue, muscle soreness, exhaustion, and/or an injury from exercising as a result of engaging in the prescribed physical fitness exercises. We do not anticipate that these risks are more than what this population experiences in their regular fitness routines.

Neurocognitive Assessment: Neurocognitive assessments are designed to be challenging in order to capture peak performance. Subjects may experience frustration and anxiety over performance as they proceed through the assessment.

Physiological Assessments: Physiological assessments are designed to be challenging in order to capture physiological condition. Subjects may experience anxiety, fatigue, nausea, dizziness, skin rash and/or irritation from sensors on wearable devices. Risks of the mock CFT include: muscle strain from overuse of a specific muscle, lower back pain due to poor form, and the chance of dehydration or heat exhaustion on hot days

Warfighter Performance Assessment: work performance evaluation may be a sensitive topic for this population. Participants will be asked during the consent process if they give permission for the study team to contact their direct supervisor. If participants do not want their supervisor contacted, then the M-ADL will not be administered. If participants are okay with supervisors being contacted the supervisors will fill out a blank survey and return it to the researchers. Participants will not see their supervisors responses, and supervisors will not see any of the participant's study data.

Symptom Measures: In order to create a complete picture of symptoms and external factors affecting recovery we will administer measures that ask for personal information such as

emotional state, combat exposure, and childhood experiences. Due to the sensitive nature of the questions, subjects may experience some discomfort while completing these measures.

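### Section 13.6 lets the investigator end study participation, and with it outcome follow-up, for inability to comply or lost eligibility, which conflicts with follow-up of every randomised participant and with ITT

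*Protocol*

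**What the plan says.** Protocol Section 13.6, after describing withdrawal of consent, gives the principal investigator a separate power. The investigator "may terminate participation in this research study at any time if he determines this to be in a participant's best interest". Two further grounds are added in the same sentence: "or if a participant is unable to comply with the procedures required, or if they no longer meet eligibility criteria". What ends is participation in the research study. The section does not mention stopping sessions while continuing assessments.

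Other sections bear on this:

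- **Section 10.1** schedules further evaluations for each participant randomised to either arm, after the last treatment session and again at 3 months. Assessments take place at three time points only: pre-treatment, post-treatment and 3 months post-treatment.
- **Section 11.6**: "Analyses will be based on intention to treat (ITT").
- **Section 11.1** relies on multilevel modelling for missing follow-up data. Section 11.5 allows for 20% attrition.
- **Section 12.5**, on symptoms: "Participants will endorse atypical neurobehavioral symptomatology compared to published normative data". The primary hypothesis in Section 9.3 uses the same scale: "There will be a greater reduction in the Neurobehavioral Symptoms Inventory (NSI) from pre- to post-SAET compared to the control condition".
- **Section 12.6** excludes "An acute orthopedic injury that limits your capacity to complete study procedures as determined by the study Physical Therapist, PI, and/or medical record review".
- **Section 14.1** lists among the risks of the exercise programme "and/or an injury from exercising as a result of engaging in the prescribed physical fitness exercises".

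**The concern.** Intention to treat needs outcome data from everyone randomised, including those who stop the intervention. Section 13.6 can end data collection for reasons that arise after randomisation and may be related to arm or outcome. An acute injury that limits study procedures is an exclusion criterion, and injury is a listed risk of the exercise programme. Ability to sustain five one-hour sessions a week for 8 weeks may also differ between aerobic and resistance training and stretching.

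If such participants leave follow-up, the post-treatment NSI exists only for those who stayed. Whether follow-up continues is a rule of trial conduct. A statistical analysis plan can choose how to analyse missing scores, but it cannot restore scores that were never collected.

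**Working it through.** **1. Does the text allow the loss?**

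| Question | Section | Answer |
|---|---|---|
| What may be ended? | 13.6 | Participation in the study, at any time |
| On what grounds? | 13.6 | Best interest; inability to comply; eligibility no longer met |
| Is eligibility limited to entry? | 13.6 | No; the wording applies it after entry |
| Who is to be assessed? | 10.1 | Each randomised participant, after the last session and at 3 months |
| Does follow-up continue after termination? | none | Not stated |
| Analysis principle | 11.6 | ITT |

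Sections 10.1 and 13.6 give different answers for a terminated participant, and nothing says which prevails.

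**2. Which NSI value is lost?** The NSI is scheduled pre-treatment, post-treatment and at 3 months. Termination during the 8 weeks leaves only the baseline value. Termination after the post-treatment visit costs only the 3-month value.

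**3. The plan's own figure.** Section 11.5 states 85% power with 70 per arm, two-sided alpha 0.05 and 20% attrition. It gives no effect size or SD, so the 85% cannot be reproduced forward. The attrition arithmetic is consistent: 70 × 0.80 = 56 completers per arm, and 112 / 0.80 = 140. Solving backwards, d = (1.960 + 1.036) × √(2/56) = 0.566 SD. This value is used below as the assumed true effect, with a negative sign for symptom reduction.

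**4. Direction and size under assumptions.** Loss rates and outcome gaps are assumed; the protocol gives none. Estimates use completers only.

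*(a) Loss of participants who do worse, SAET only.* A share m is lost, and their mean outcome is s SD worse than that of those kept. Then −d = m(μ + s) + (1 − m)μ, so the completer mean is μ = −d − m·s.
- m = 5%, s = 0.5: −0.566 − 0.025 = −0.591.
- m = 20%, s = 1.0: −0.566 − 0.200 = −0.766.

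The effect is inflated.

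*(b) Loss of participants who improve by at least 1 SD, same rule in both arms.*
- All removed: SAET loses Φ(−1 + 0.566) = 33% and its completer mean is −0.022. SCG loses Φ(−1) = 16% and its completer mean is +0.288. The difference is −0.022 − 0.288 = −0.31.
- Half removed: losses of about 17% and 8%; difference −0.48.

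The effect is diluted.

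*(c) Pattern (a) in NSI points with no true effect.* Assume that those removed would have improved 8 points less than those kept. Eight points is the protocol's threshold for clinically relevant change, borrowed here only as a scale. Bias = 8(f₁ − f₀), and SE = SD × √(1/n₁ + 1/n₀) with n = 70(1 − f). At SD 14:
- 20% v 0% removed: bias 1.6; SE = 14√(1/56 + 1/70) = 2.51; two-sided rejection rate 9.8%.
- 20% v 10% removed: bias 0.8; SE = 14√(1/56 + 1/63) = 2.57; rejection rate 6.1%.

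Across SD 10 to 20 the first case runs from 14.5% to 7.3% and the second from 7.2% to 5.5%.

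**5. Can the multilevel model repair it?** A likelihood-based multilevel model handles loss that depends on data it has seen. For a loss at 3 months, the post-treatment NSI is available. For a loss during treatment it has only the baseline NSI and the arm. It cannot then correct loss driven by the unobserved post-treatment state.

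**The case against.** The best defence is that Section 10.1 already sets both evaluations for each randomised participant, timed from the last session and not from completion of 40 hours. Section 13.6 is permissive, and its wording is inability to comply, which is narrower than non-compliance. The intervention is adapted for orthopedic limits, both arms have the same weekly schedule, and Section 14.1 expects exercise risks no greater than those of this population's usual fitness routines. Differential loss is therefore possible but not shown. All of this stands, and it limits how strongly the point can be put. It does not settle which section prevails for a terminated participant.

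Three stronger readings are tempting, and the documents do not support them.

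- **Recovered participants will be removed.** Read literally, a participant whose NSI returns to the normal range no longer meets Section 12.5. But the protocol nowhere states that recovery ends participation, and recovery is the aim of the trial. With no NSI scheduled during treatment, the criterion would ordinarily first be failed at the post-treatment visit. The main cost would then be the 3-month value, with loss depending on a score already observed.
- **The analysis will be per-protocol under an ITT label.** Nothing says that terminated participants leave the analysis set.
- **The type I error will be about 10%.** That figure rests wholly on assumed inputs and models inflation only. Pattern (b) goes the other way.

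**Conclusion.** The point holds as a conflict between sections with a statistical consequence. Section 13.6 permits the end of all study participation on post-randomisation grounds. It does not preserve outcome assessment, and it is not reconciled with Sections 10.1 and 11.6. The exposed quantity is chiefly the post-treatment NSI of participants terminated during the 8 weeks for injury or inability to comply.

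Bias arises only if such losses differ by arm and depend on outcomes not observed. The documents fix neither direction nor size. The illustrations, from -0.31 to -0.77 SD around an assumed -0.57, show only that it could go either way and be material. The multilevel model is a partial safeguard. This is an inexpensive improvement that should be made; it does not show that the trial's result will be wrong.

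**What to change.** Reconcile Section 13.6 with Sections 10.1 and 11.6 by stating that:

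1. for purposes of follow-up, eligibility is judged at enrolment;
2. ending study sessions for any reason other than withdrawal of consent does not end outcome assessment;
3. participants whose sessions have ended are still invited to the post-treatment and 3-month evaluations and stay in the ITT analysis;
4. the reason and date for stopping sessions, and for any missed evaluation, are recorded by arm.

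The clinical grounds for stopping sessions are not affected and can stay as written. The sample size does not change.

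The cost is a short protocol and consent amendment, plus the staff effort of following up participants who have stopped attending. The evaluations themselves are already scheduled for every randomised participant. The protocol gives only total funding, so whether this follow-up effort is budgeted cannot be judged. The change must be made prospectively, because missed assessments cannot be recovered later.
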